## **PROCESS OF RECRUITMENT**

---

### **PREPARATION FOR THE RESEARCH AUDIT CLINICS**

---

1. A clinic coordinator will be identified from each cleft centre to liaise with the research team regarding the arrangements for jointly agreed data collection days.
2. Before the clinic visit, at each cleft centre, the clinic coordinator together with the clinical director and the research team will identify the assistance required by the cleft team in order to achieve intended outcomes from the research audit clinic:
  - a. Key personnel will be identified for each of the stations in the research audit clinic.
  - b. Facilities will be arranged for the research audit day.
3. Each cleft centre will identify eligible participants at their centre using the inclusion and exclusion criteria. They will then agree dates for clinics and numbers likely to attend each of these clinics. This will be verified by comparison with a list extracted from the CRANE database.
4. The Cleft centre will send out an invitation to eligible participants to attend a research audit clinic. All invited parents/guardians and children will receive an information letter and information sheet about the research explaining the purpose of the study and what will happen during the research audit clinic day. Participation in the study will be completely voluntary .
  - a. Information letter to the parent/guardian (Appendix 9)
  - b. Information sheet to the parent/guardian (Appendix 10)

5. Each child's parent/guardian should also be contacted by telephone by the clinic coordinator during the week before the data collection day to confirm that they will be able to attend and ask if they have any questions about the research. Children who are unable to attend on the date offered will be offered an alternative date.
6. The cleft centre will provide the research team with a list without personal identifiers of the eligible participants that have been scheduled for the research audit clinic.
7. The Research Team will prepare the following for each participant;
  - a. Route map to the child, which explains in pictures what will happen during the day. (Appendix 11)
  - b. A "goody bag" for each child containing a small colouring book, colour pencils, a biro for the parent, a small teddy bear.
  - c. A thank you letter to parent/guardian (Appendix 12)
  - d. A consent form (Appendix 13)
  - e. An individual envelope containing:
    - i. Labelled data capture forms
    - ii. A "satisfaction with service" questionnaire for completion by parent/guardian.
    - iii. A "health and lifestyle questionnaire" for completion by parent/guardian.
    - iv. A labelled plastic bag and lab-card for impressions or box for duplicated models and wax bite.
    - v. A labelled free post envelope for its return.

## PROCEDURE ON THE RESEARCH AUDIT CLINIC DAY

---

1. A member of the research team will meet with the cleft team before the research audit clinic starts to review the arrangements for the day and deal with any last minute issues or concerns.
2. The research team, when possible, will display signs for the different “stations” where the child will be examined. The signs will match the figures in the child’s folder: “Listening test”, “Speaking test”, “Moulds”, “Dental Check-up”, “Height and weight” and “Photos”.
3. The research team will prepare the the following for the research clinic audit.
  - a. Assembly of the measuring station.
  - b. Ensuring that all administrative material is in order.
  - c. Providing a box for parent/guardian for the anonymous return of the questionnaire on satisfaction of service .
4. On the day of the scheduled audit, the parent(s) and their child will be asked if they are willing to participate in the study and whether they have any questions. The questions will be answered by a member of the research team. If the parent refuses to participate in the study, they will be informed that data obtained during the clinical examinations will only be stored in their medical file and that researchers will have no access to them. They will also be informed that their decision will have no impact on their current or future clinical care. If it is not possible for the research team to attend, the clinical team will seek and obtain consent.

5. Eligible parent/guardian will be able to sign the consent form and the child will be asked for verbal consent.
6. The research team will prepare the identification labels for the forms used at the different stations.
7. Each child will be given their own personal envelope folder together with a “goody bag” by a member of the research team or clinical team. The folder will contain the “route map” (Appendix 11) showing the different stations they will visit during the day. The route map will be explained to the parent and the child by a member of the research team or clinical team.
8. Children will visit each station with their parent/guardian. Once the child has had records taken the appropriate member of staff should sign the “route map” provided in the folder before the child proceeds to the next station. The parent or child can withdraw from any section/part of the clinic at any time.
9. When all the measurements have been taken, the research staff will collect the envelope folder from the child and check that all sections of the "route map" have been signed. They will also check that all records have been collected and that the relevant data capture forms are stored in the child's individual folder.
10. The parent will be asked to complete the satisfaction of service questionnaire, they can complete the questionnaire at the centre by dropping it in the questionnaire box provided or they can mail it back in the free post envelope provided to them. A member of the research team or clinical team will also provide each set of parent/guardian a labelled copy of the health and lifestyle questionnaire together with a free post

envelope. Parent/guardian will be asked to complete the questionnaire in their home environment and send it back to the researchers in the prepaid envelope.

11. The child will then be given a “small teddy bear” and their parent/guardian will be given a letter thanking them for attending.
12. The Research Team will collect all participants’ folders at the end of each research audit clinic together with the research questionnaire; audio and video tapes or digital recordings; photographs, impressions for study models or study models and data capture forms. The research team will be responsible for the correct labelling of all data forms and items.

## **DATA COLLECTED FROM THE CLINICAL RECORDS AND RESEARCH AUDIT CLINIC**

### **SPEECH ASSESSMENT**

#### **Method**

Each centre will nominate one speech and language therapist (SLT) to be the designated contact person for the study at each surgical site

1. In advance, this SLT will identify the locations and therapists who have reviewed or provided treatment for the child. The SLT will complete the therapy background information form using information in the medical records and the team based speech and language therapy notes, and by liaison with local services when appropriate.
2. At the clinic, parent/guardian will be asked to confirm details at the time of the audit on the speech treatment history which has been collected on the therapy background information form.
3. For the assessment, speech audio video recordings will be collected on all subjects using the equipment, procedures and speech sample as described by Sell et al., 2009 (17) (or its equivalent) from the 5-year-old study cohort. All the recordings will be made by one of the centre based SLTs, who has been Cleft Audit Protocol for Speech-Augmented (CAPS-A) trained. Recordings are to be made in a quiet room with the subject facing natural light if possible. Each child will sit in front of a pale grey background, supplied by the research team. The microphone will be placed on a stand, 23 -30 centimeters away from the child, at the level of their mouth and placed to one side. The face and upper neck will be framed in the picture. The speech sample material will be presented beside the camera at the subject's eye level. Following data collection the SLT will check, using

the headphones, that a high quality sample has been recorded. The SLT will document the tape number on the Therapy Background Information Form.

The speech sample will include:

- 1) A sample of 2 minutes of conversation: according to Sell et al 2009 (17). Encouraging open-ended questions through a progression of questions on a particular topic is advised.
- 2) Counting from one to twenty and from 60 to 70.
- 3) Saying (not singing) a nursery rhyme e.g. Jack and Jill.
- 4) Repetition of each of the 16 sentences after the therapist using the Great Ormond Street Speech Assessment (GOS.SP.ASS.) picture book.

#### Equipment

- Therapy Information Form (Appendix 14)
- The Great Ormond Street Speech Assessment (GOS.SP.ASS.) picture book.
- Video cameras with microphone, microphone stand, headphone, spare batteries, tripod, pale grey background and means to hang, DV tapes, sticker for reward, sticker to mark completion of station to be inserted in child's route map
- The research team will copy the recording in accordance to the prior arrangements established with each cleft team. The master copies will remain at the Centre and the copies will be passed to the research team.

#### Personnel

The speech and language therapist at each cleft centre. The Speech Steering Group ([name], [name], [name]) together with the research team will advise on data collection and through their networks ensure all the centres are clear with regards to the protocol. Speech

outcome data at the time of the assessment will be collected by the local team according to their local protocol. For example some centres use the Great Ormond Street Speech Assessment (GOS.SP.ASS.) clinical tool at this assessment for the purposes of collecting comprehensive clinical data (18, 19). Others use CAPS-A as the speech audit tool (20). For this outcome study, the process of analysis will be conducted once all the data from all the centres is collected. All the samples will be placed in a randomised order onto DVDs. Analysis will be undertaken by independent listeners. 10% of the cases will be analysed for inter- and intra-rater reliability.

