### **RATIONALE**

---

This survey follows the protocol used in the original CSAG survey which attempted to locate and study all children born with non-syndromic UCLP in defined periods. In addition, the survey will also examine if children with cleft have the same growth development as children without a cleft and examine the psychosocial predictors of outcome such as social and family circumstances, parenting and parental characteristics and child characteristics.

To ensure that we are comparing a similar group of children in the UK, the current study is an observational cross-sectional study of 5-year-olds with UCLP. It is not necessary to survey all children in the UK born with some form of clefting as several multi-centre comparisons have provided evidence that care for and outcomes in, UCLP cases are representative of cleft care across the UK. All of the 5-year-olds born with UCLP in the current study will have been treated within a centralised or centralising service. By the age of 5, children in the UK will have started their formal education and will be speaking to people they are unfamiliar with. Centralized multidisciplinary cleft care teams throughout the U.K. have developed at different rates and have differing models of centralized care. This will allow us to compare differences in the timing of centralisation and a number of different models of care.

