### **STUDY SAMPLE**

---

We aim to study all 5-year-old children from cleft centres in the UK born in the two year period between **01/04/2005 to 31/03/2007**. At the time of the audit the child should be aged between 5 years 3 months and 5 years 9 months. The original CSAG survey identified 326 five-year-olds born with UCLP in the UK over a two year period and outcome records were collected

for 239 five-year-olds (1). This represents a recruitment rate of 73%. As care is now centralised and better documented we anticipate that we will be able to obtain information from at least 250 patients born with with UCLP.

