### OUTCOME MEASURES FROM RESEARCH AUDIT CLINIC AND CLINICAL RECORDS

- Inter-arch relationships measured with the 5 year old index and potentially the 4 scale index developed in Manchester.

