### Method

The assessment of facial aesthetics will follow the recommended guidelines for photography of cleft audit patients (22, 23). The child will be asked to sit on a chair placed 0.5 metres in front of a standardised black or white non-reflective background which has been mounted on a wall, or a plain wall can be used as background. The hair will be arranged to show the entire ear.

The following views will be taken for each child with the lens length fixed to give standardised magnification.

1. Left lateral face (1:8)
2. Right lateral face (1:8)
3.  $\frac{3}{4}$  left lateral face (1:8)
4.  $\frac{3}{4}$  right lateral face (1:8)
5. Facial (1:8)
6. Facial smiling (1:4)
7. Whistling (1:4)
8. Worm's eye view (1:4)
9. Lip & Nose (1:3)

Each photograph will be catalogued and recorded for each patient

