## **POWER CALCULATIONS**

---

In the baseline survey of outcomes in five year old children with CLP nearly 40% had poor dental arch relations; 40% had untreated dental caries and 19% were judged to be impossible to understand or were just intelligible to strangers. With a sample size of 250 children and setting the (2-sided) value of alpha at 0.05 we will have over 90% power to detect an absolute difference in dental arch relations and caries of 20% and over 80% power to detect an absolute difference in intelligible speech of 10%.

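### The comparison with the 1998 CSAG grades has no stated link between the current raters and the 1998 raters, so a shift in grading threshold would look like a change in outcome

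*Protocol*

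**What the plan says.** The second item under Objectives is to describe outcomes in five-year-olds and compare them with the original CSAG survey. Statistical Analysis makes this comparison by regression against outcomes observed in 1998, controlling for confounders, and reads the result as the effect of centralisation. Power Calculations names three outcomes: poor dental arch relations, untreated caries and poor intelligibility. The first and third are graded by judgement. Facial appearance on the Five Point Scale is a further graded outcome, but it is not powered.

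For speech, the Method section takes recordings from the current five-year-old cohort. The Personnel section starts the analysis once data from all centres are in and then states: "All the samples will be placed in a randomised order onto DVDs. Analysis will be undertaken by independent listeners". It adds inter- and intra-rater reliability on 10% of cases.

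For dental models, the outcome is "Inter-arch relationships measured with the 5 year old index and potentially the 4 scale index developed in Manchester". For photographs, the scale is named. Neither section says who grades, in what order, or which records make up the rating set. The only calibration statement in the Protocol concerns the paediatric dentists or therapists (Assessment of Dental Health, Personnel). It is for the current project and has no stated tie to 1998 examiners.

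**The concern.** In a before/after comparison of graded outcomes, the recorded difference is the true change plus any difference between the two panels' thresholds. If one panel grades every current record and another graded every 1998 record, survey and panel are fully aligned. No covariate in the regression can then separate the two parts, and a larger sample only estimates their sum more precisely.

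The speech safeguards address other problems. Random order protects against drift within the session. Independent listeners protect against local loyalty. The 10% check (about 25 of 250 cases) measures agreement among current listeners. A panel could agree perfectly with itself and still be uniformly more lenient or stricter than the panel of 1998. What is at stake is whether a change in poor speech or poor dental arch relations can be credited to centralisation.

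**Working it through.** **Inputs.**
- Test level, from Power Calculations: "setting the (2-sided) value of alpha at 0.05".
- Current sample, from the same section: "With a sample size of 250 children".
- CSAG sample, from Study Sample in the survey methods: outcome records "for 239 five-year-olds (1). This represents a recruitment rate of 73" per cent (239/326 = 73.3%).
- Poor intelligibility in CSAG: 19% (Power Calculations).
- Poor dental arch in CSAG five-year-olds: 36% (Background). Power Calculations says nearly 40%.
- Drift sizes: assumed, because the Protocol gives none.

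**Formula.** Two-sided test of two proportions with n1 = 239 and n2 = 250. Write d = p1 − p2 and p̄ = (239·p1 + 250·p2)/489. SE0 = √[p̄(1−p̄)(1/239 + 1/250)] and SE1 = √[p1(1−p1)/239 + p2(1−p2)/250]. Probability of significance = Φ[(d − 1.96·SE0)/SE1] + Φ[(−d − 1.96·SE0)/SE1].

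**The plan's own figures first.** 40% to 20% gives 99.8%, and 19% to 9% gives 89.3%. The stated values of over 90% and over 80% therefore hold for improvements of these sizes. The power statement is not the problem here.

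**Speech, no true change, graded rate 5 points lower.** p1 = 0.19, p2 = 0.14, d = 0.05, p̄ = 0.1644, SE0 = SE1 = 0.0335 to four places. The first argument is −0.469, so Φ = 0.320; the second term is negligible. The result is 32%.

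**Dental arch, no true change, 20% of poor cases relabelled as not poor.** p2 = 0.36 × 0.8 = 0.288, d = 0.072, p̄ = 0.3232, SE0 = 0.0423, SE1 = 0.0422. The first argument is −0.259, which gives 0.398, about 40%.

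**Range of assumed shifts (probability of significance, no true change):**

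| Downward shift (points) | Intelligibility, 19% | Dental arch, 36% | Dental arch, 40% |
|---|---|---|---|
| 0 | 5% | 5% | 5% |
| 3 | 14% | 11% | 11% |
| 5 | 32% | 22% | 21% |
| 8 | 70% | 48% | 45% |
| 10 | 89% | 67% | 64% |

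Whether 36% or 40% is used as the dental arch baseline hardly matters. Relabelling 10% or 30% of poor dental arch cases, instead of 20%, gives false improvements of 3.6 and 10.8 points, significant about 13% and 74% of the time. A 10-point shift in intelligibility gives 89%, the same as the power for the 10-point target difference, because the test cannot tell the two apart.

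**Drift the other way.** With no true change, a panel 5 points stricter on intelligibility (19% to 24%) gives a significant apparent worsening about 27% of the time. If the truth were 19% to 9% and the panel graded 14%, the chance of detecting the improvement would fall from 89% to 32%, by the same calculation as above.

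**The case against.** Much can be said on the other side, and part of it stands.

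- **Models and photographs.** A reader might infer that these are graded without 1998 records, unmasked and in no set order. The Protocol does not say so; it describes no grading session for them. Raters, order and masking may sit in an analysis plan or rating manual that is not shown. This stands. For these outcomes the point is only that the Protocol makes no provision for a link to the 1998 grades.
- **Same method as CSAG.** The survey Rationale says "This survey follows the protocol used in the original CSAG survey". A reader might see a contradiction because the speech recording procedure cites a 2009 paper. The documents do not support that. The sentence allows an equivalent procedure, and the sentence-repetition task uses the GOS.SP.ASS. picture book, a tool first referenced to 1994. CAPS-A is cited as one centre-level option, not as the listeners' tool. Publication dates do not show that the speech sample changed. Equally, following the same protocol does not calibrate a new panel to an old one.
- **Published rates.** A reader might assume that only published 1998 rates will be used. The Statistical Analysis wording fits individual-level data at least as well. Individual data would still carry the 1998 panel's grades.
- **Size.** The shifts are assumed, and their direction is unknown. This stands.
- **A generic limit of historical controls.** True, but for speech the rating set is fixed in the Protocol, and what is rated cannot be repaired in the analysis afterwards.
- **Archive and masking.** No retained CSAG material is mentioned, and old recordings might be recognised by their format. This stands, so the remedy needs a fallback.

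**Conclusion.** The concern holds in limited form, as something the plan should change rather than as an arithmetical error. For speech, the stated rating set contains only current recordings, and no stated safeguard can detect a shift from the 1998 thresholds. For dental models (a powered outcome) and photographs, the Protocol provides neither re-rating of nor calibration to 1998 records; that they are graded without such records is not established.

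The size is illustrative: 32% false significance for a 5-point shift in intelligibility and about 40% for relabelling one poor dental arch case in five, against 5%. These figures assume no true change, 239 against 250 children, unadjusted proportions and the stated drift. They also assume that intelligibility is graded by the same independent listeners, since the speech outcome list does not name it. Drift in the other direction could hide a real improvement.

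A reader might also infer that the permitted variation in photograph background tells raters which centre a child attended. That is possible but not shown: nothing ties background to centre or says what raters would know.

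**What to change.** 1. **Speech Assessment, Personnel.** Where CSAG five-year-old recordings survive, add a relabelled random sample of them to the randomised set given to the independent listeners.
2. **Models and photographs.** Do the same when these are graded.
3. **Statistical Analysis.** Use the current panel's grades of the CSAG records, set against their 1998 grades, to estimate the threshold shift, and correct or bound the 1998 comparison for that outcome.
4. **Fallback.** Where no records survive, or where format makes old records recognisable, report that outcome's 1998 comparison with a sensitivity analysis giving the rater shift, in either direction, that would overturn the conclusion.
5. **Optional.** Crop photograph backgrounds before rating, since the Method allows a "standardised black or white non-reflective background which has been mounted on a wall, or a plain wall can be used as background".

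The cost is retrieval effort and some extra rating hours for the existing panel, with no further procedure for any child. Archive availability is an assumption; the fallback needs no archive.

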#### OUTCOME MEASURES FROM CLINICAL RECORDS AND RESEARCH AUDIT CLINIC

- Assessment of, history of and current speech and language therapy intervention in 5-year-olds, including: patterns of SLT delivery, availability of speech therapy treatment when required, analysis of amount of SLT contact time, methods of SLT delivery, foci of therapy and assessment of residual needs for speech and language therapy (numbers that require SLT intervention, but have not received it or have received insufficient therapy).
- Nasality (hypernasality, hyponasality), Nasal airflow (nasal emission, nasal turbulence), Speech Cleft Characteristics, Developmental Immaturities.

## AUDIOLOGY ASSESSMENT

---

### Method

An Audiologist or Audiological Physician (including a Paediatrician with a special interest in Audiology) / ENT surgeon will conduct the data-collection at each research audit clinic.

1. The audiologist and/or member of the research team will examine the clinical records (prior to the audit clinic) and record information on the data capture form.
2. Parent/guardian will be asked to confirm details of previous ENT assessments and episodes of treatment, including the insertion of grommets, undertaken for their child.
3. Standardised Pure Tone Audiometry thresholds (BSA guidelines) using an audiometer and a tympanometer will be undertaken for each participant by the local Audiologist.

